4- Patients satisfaction in achieving their goals after the procedure as assessed by Goal Attainment Scale³⁸. Based on this scale participants will be asked for 3 main goals that they desire to achieve after the intervention. The baseline score will be (-1) and they will be interviewed again at 1, 3, 6, 9 and 12 months, to record how they reported their achievement. The scores of (-2), (-0.5), (0), (1) and (2) will be assigned if they feel that their condition is worse than before, better but not as good as expected, as expected, better than expected and much better than expected. All goals will be weighted equally, and final score will be calculated based on the available formula, in each session. The higher score is presenting of better outcome.

Secondary Objective:

1- Upper limb function changes as assessed by Box and Block test. Participants will be in sitting position and will be asked to move the cubes from one part to the other part in 1 minute. The test will be done in baseline and in 1, 3, 6, 9 and 12 months.

2- Changes in pain as assessed by Brief Pain Inventory Questionnaire. This is a self-administered questionnaire that will be provided for participants for filling out at baseline and in 1, 3, 6, 9 and 12 months after the intervention. The Patient will ask to answer each question by choosing a number between 0 to 10, and the final score is calculating by adding these numbers together and then divided by 4. The result will show the severity of patient pain out of 10. (0 means no pain and 10 means the worst pain that can be imagine)

3- Changes in the Hand resting position as assessed by Keenan Scale (1987)³⁶. Participants will be assessed by an independent examiner and based on available scale their hand position will be graded. Grade 1 is the minimum deformity while grade 5 is the maximum deformity which is presented by clenched fist and palmar hygiene problem. The assessment will be done at baseline and in 1, 3, 6, 9 and 12 months.

4- Changes in thumb deformity (position of thumb in relation to other fingers) as assessed by House Scale (1981)³⁵. Participants will be assessed by an independent examiner and based on available scale their thumb position will be graded between 1 to 4. Grade 1 is the minimum deformity and 4 is the maximum deformity. The assessment will be done at baseline and in 1, 3, 6, 9 and 12 months.

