The protocol follows the same assessment and preparation as cryoneurotomy. [name] has performed thousands of these interventions to nerves. They are also percutaneous nerve procedures. The protocol is quite similar as cryoneurotomy, with the exception of the probe. Pulsed radiofrequency (PRF), a technique introduced in the 1990's³³, is known to be safe and effective on nerve structures and particularly relieving pain. It delivers an electrical field and heat bursts to targeted nerves or tissues without damaging these structures. Previous studies have used continuous radiofrequency (CRF)³⁴ exposes target nerves or tissues to a continuous electrical stimulation and ablates the structures by increasing the temperature around the RF needle-tip. PRF does not produce sufficient heat to cause structural damage. The availability of cryoneurotomy is quite limited to the lack of machines in Canada, where as radiofrequency is widely performed in hospitals and clinics all across Canada. To date our availability of time on the cryoneurotomy equipment is limited, and pulsed radiofrequency will allow for shorter waits.

Sample Size Justification. Statistical Analysis

Sample Size: N = 50

This is a pilot study. A convenience sample of 50 patients is anticipated, based on the volume of patients that has been triaged in this clinic to date. Over 100 patients have been triaged in 18 months, so it is anticipated that 50 target patients to be fully completed treatment in 18 months. At 4-6 (divided between surgical and interventional) patients per month for 12 months, this is achievable based on this clinical experience. Analysis will be individualized per patient, as each will undergo a unique procedure. Statistical analysis will address each patient stream individually. The outcome measures that will used are standard clinical and functional measures, but effect sizes are not readily available from previous studies in order to formally calculate sample size. Furthermore, this study uses an exploratory prospective cohort design, rather than a parallel group trial design, limiting the rationale for providing a sample size calculation.

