To confirm that improvements in outcomes are statistically significant a paired t-test on the difference of proportions, applicable to pre-treatment and post-treatment, will be performed. Pearson's correlation and logistic regression will also be used to determine whether any key predictors are associated with any of the outcomes at final visit. We will employ repeated measures or linear mixed (multilevel) models of change to analyze within-person trajectories in all key outcomes for the intensive repeated measures data spanning the 12-month study period. Such models derive individual parameter estimates for baseline function and change pursuant to nerve or surgical procedure, and will directly index the magnitude in improvement for each outcome (pursuant to treatment) with each individual serving as their own control (i.e., with change indexed relative to each individual's own personal baseline).

If normal distribution in the outcomes does not stand, McNemar's test and Spearman correlation will be calculated instead of paired t-test and Person's correlation, respectively.

We will rely on Island Health Statistic for this process, the data will not leave Island Health and will be analyzed through REDCap. (Statistics provided by [name], Island Health)

Inclusion Criteria:

- Adult patient \geq 18 years old, with upper extremity spasticity causing functional impairment.
- Patients that have plateaued in outcomes in which the clinical examination suggests further interventions can be trialled.
- The clinical examination, including a V1 (maximal passive stretch) and V3 (Fast catch) on upper extremity examination that demonstrates further passive or active range may be possible, versus if contracture must be managed. For example, a fistled hand that can be forced open. This includes factors such as fluctuating tone or clonus interfering with assessment.
- The patient undergoes a diagnostic nerve block to determine if there is a reducible spasticity in the muscle versus contracture.
- The patient has been offered a neuroablative procedure or surgery and has elected to undergo the procedure. The patient has consented to undergo said procedure.

Exclusion Criteria:

[figure not shown]
- Patients where no consent or Assent is obtained
- Unable attend treatment schedule

Efficacy Evaluation/Schedule/length of the study:

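### Goal Attainment (primary objective 4) has no listed follow-up code for an unchanged goal, and its assigned baseline of -1 does not fit the individual-baseline mixed model planned for all key outcomes

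*Combined protocol and SAP*

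**What the plan says.** Goal Attainment is the fourth of four primary objectives and is described there as patient satisfaction, which the Hypothesis section also names. Each patient sets three goals. The start value is assigned, not measured: "The baseline score will be (-1"). At 1, 3, 6, 9 and 12 months the patient is interviewed again: "The scores of (-2), (-0.5), (0), (1) and (2) will be assigned if they feel that their condition is worse than before", then "better but not as good as expected, as expected, better than expected and much better than expected". Five scores are paired in order with five labels. Goals have equal weight, and the "final score will be calculated based on the available formula, in each session"; the formula is not written out.

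The section Sample Size Justification. Statistical Analysis plans a paired pre/post test and also repeated measures or "linear mixed (multilevel) models of change to analyze within-person trajectories in all key outcomes". It adds: "Such models derive individual parameter estimates for baseline function and change pursuant to nerve or surgical procedure", "with change indexed relative to each individual's own personal baseline". No exception or separate analysis is stated for Goal Attainment. The same section says "This is a pilot study".

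**The concern.** There are two separate difficulties.

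1. **Coding.** Every goal starts at -1, but -1 is not among the follow-up scores and no label means that nothing has changed. An assessor who follows the list must call such a goal worse or better. That answer is foreseeable: the eligibility criteria select patients whose outcomes have plateaued, and the cryoneurotomy section allows for nerve re-growth. A missing option cannot be reliably recovered once the interviews are over.

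2. **Constant baseline.** Three equally weighted goals at -1 give every patient the same baseline score. The model text promises individual estimates of baseline function, but here there is no between-patient variation to estimate. If the assigned value is entered as a sixth measured visit, the model treats a constant as a noisy observation, and the standard errors for change from baseline can be wrong. This holds however the first difficulty is settled.

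**Working it through.** The plan has no figure to reproduce here. The sample size of 50 is a convenience number, and nothing below depends on it.

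**Coding.** Inputs from Primary Objectives, item 4: baseline -1; follow-up scores -2, -0.5, 0, 1, 2. Change = follow-up score minus (-1).

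| Label | Score | Change |
|---|---|---|
| Worse | -2 | -1 |
| Better, below expectation | -0.5 | +0.5 |
| As expected | 0 | +1 |
| Better than expected | 1 | +2 |
| Much better than expected | 2 | +3 |
| Unchanged | none listed | 0 is not available |

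Let u be the share of goals unchanged, q the share of those that staff keep at -1 anyway, and p the share of the rest coded -0.5 (the others -2). The mean change per goal shifts by u(1 - q)[0.5p - (1 - p)] = u(1 - q)(1.5p - 1). The shift is zero if q = 1 or p = 2/3, positive for larger p and negative for smaller p. The documents give none of these shares. Purely as an illustration, at an assumed u = 0.3:

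- q = 1: zero
- q = 0.5: -0.15 to +0.075
- q = 0: -0.30 to +0.15

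These are ranges of possible miscoding on the raw goal scale, not estimates of bias.

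**Constant baseline.** Assumptions, none given in the documents: n patients; visit fitted as a factor; baseline variance 0; five follow-ups with equal SD s and equal correlation r; no missing visits; the -1 entered as a sixth measured visit. Because the baseline is constant, the true variance of the mean 12-month change is s²/n.

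*Random intercept only.*
- Expected subject mean square: 6 × (5 + 20r)s²/36 = s²(5 + 20r)/6.
- The six visit variances sum to 5s², so the expected residual mean square is [5s² - s²(5 + 20r)/6]/5 = s²(5 - 4r)/6.
- Intercept variance: the difference of the two divided by 6, which is (2r/3)s².
- Model variance of 12 months minus baseline: 2 × residual/n = s²(5 - 4r)/(3n).
- SE ratio (model/true): sqrt((5 - 4r)/3).

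*Random intercept plus random pre/post change.*
- The fitted intercept variance is 0. The common residual averages four follow-up contrasts with variance s²(1 - r) and one baseline term of 0, giving 0.8(1 - r)s².
- Model variance of 12 months minus baseline, times n: s²(0.2 + 0.8r) for the follow-up mean, plus 0.8 × 0.8(1 - r)s² for the 12-month deviation, plus 0.8(1 - r)s² for the baseline. The sum is s²(1.64 - 0.64r).
- SE ratio: sqrt(1.64 - 0.64r).

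*Random intercept plus linear slope.* Solved numerically from the large-sample likelihood under the same assumptions.

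| 12-month SE ratio (model/true) | r = 0.2 | r = 0.5 | r = 0.8 |
|---|---|---|---|
| Random intercept only | 1.18 | 1.00 | 0.77 |
| Plus linear slope | 1.22 | 1.07 | 0.88 |
| Plus random pre/post change | 1.23 | 1.15 | 1.06 |

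| Reported between-patient baseline SD (true value 0) | r = 0.2 | r = 0.5 | r = 0.8 |
|---|---|---|---|
| Random intercept only | 0.37s | 0.58s | 0.73s |
| Plus linear slope | 0.21s | 0.39s | 0.51s |
| Plus random pre/post change | 0 | 0 | 0 |

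**Paired comparison.** Subtracting a constant leaves the variance of the 12-month score unchanged, so a paired pre/post comparison reduces to a one-sample comparison with -1. It is not harmed by the constant baseline.

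**The case against.** On coding, -1 lies between the score for worse and the first score for better, so it already reads as the patient's starting state, and staff may well keep it for an unchanged goal. The cited scale, the form and the formula were not available for this review and may say so. That stands as the likely intention. It does not settle the matter, because the available text pairs scores and labels one to one without that option. A reader might infer that the gap inflates apparent benefit. The documents do not support this: the shift can take either sign, and it is nil if -1 is kept.

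On the model, a fixed starting value can be a deliberate feature of goal scaling. Goals are the patient's own, and change from -1 is well defined, so it would go too far to say that change or follow-up trajectories cannot be estimated. Only between-patient baseline variation, and with it a meaningful individual baseline estimate, is lost. The paired test, which the plan uses to confirm statistical significance, is untouched by this point.

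A reader might also infer that the mixed-model intervals will be too narrow. The documents do not support that either. The plan speaks of individual change as well as individual baselines, so a random intercept alone may not be what is meant. With a random pre/post change the intervals are too wide at all three values of r, and no false baseline spread appears. With a linear slope, part of the problem remains. The random effects are not specified and r is unknown, so the direction cannot be stated.

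**Conclusion.** The point holds as a minor one: the plan is wrong as written on two details of one primary outcome in an exploratory pilot.

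That the text lists no code for an unchanged goal, and that the baseline does not vary between patients, follows from the wording and needs no assumption beyond three equally weighted goals per patient. The size of the consequences does rest on assumptions. For coding, the literal error is +0.5 or -1 per unchanged goal, with no basis for a study-level figure. For the mixed model, the 12-month ratios of 0.77 to 1.23 cover three plausible random-effects structures at r from 0.2 to 0.8. They apply only if the assigned -1 is entered as a measured visit, and they assume equal follow-up SD, equal correlation and complete visits. They show that the standard errors can be wrong in either direction; they do not predict the error in this study.

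**What to change.** 1. In Primary Objectives, item 4, and on the interview form, list the follow-up options as -2, -1 (no change from baseline), -0.5, 0, 1 and 2. If the form already has the -1 option, only the protocol text needs the change.

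2. Add to the statistical analysis section: Because its baseline is assigned, Goal Attainment is analysed by modelling the follow-up scores only (1, 3, 6, 9 and 12 months) and comparing their means with -1, or with the value that the scoring formula gives when all three goals are at -1; no individual baseline is estimated for this outcome.

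The cost is one response option and one analysis sentence. Treatment, visits and sample size do not change. The first change should be in place before follow-up interviews are held.

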I. A thermal insulating catheter (#16 angiocatheter) serves as a guide and thermocutaneous protection from cutaneous frostbite.³¹ The catheter also serves as an insulator to provide optimal e-stim.

II. Small dose of local anesthesia for cutaneous and subcutaneous anesthesia; less than 1 ml of 1% lidocaine to avoid diffusion.

III. Cryoneurotomy lesions are performed juxtapositioned to the motor nerve branch using an in-plane ultrasound technique to optimally view and guide the cryoprobe tip.

IV. Two lesions are performed, either superior/inferior or medial/lateral to the motor nerve at a temperature of -60° for 3.5 minutes per lesion for a total of 7 minutes as per standard cryoneurotomy protocols.³¹

V. Should the patient experience a painful sensation, then the probe tip is re-adjusted immediately and the cryoneurotomy resumed.

VI. Care is taken to avoid any vascular structures; therefore, colour Doppler setting on the ultrasound is essential.

VII. Post-procedure, the percutaneous entry point is stabilized with pressure and sealed with skin glue and occlusive dressing applied.

5. Standardized outcome measures should be used to capture outcomes and adverse events. We recommend use the Tardieu scale 25 for documentation of maximal range in a joint with a slow stretch as V1 (maximal range of passive motion = XV1), and a power high velocity stretch as V3 (angle of catch = XV3), thus creating a spasticity angle denoted as V1–V3, the difference between the maximal slow stretch and rapid catch. The angle of paresis is calculated as V1 minus the patient's maximal active range of motion, indicating the patients active range vs the maximal range passively obtained.³² Other outcome measures that may be used include the MAS.

6. Reassessment of the patient post-procedure to readjust the spasticity management strategy and goals. Redistribution of BoNT will likely occur. Ongoing follow-up as of the patient as needed, as there is a potential for nerve re-growth and repeat procedures as needed.

Pulsed radiofrequency Stream

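### Goal attainment (primary outcome 4) is scored by feeling against an expectation that the plan does not say is written down or held fixed, so the score can move with no change in the patient

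*Combined protocol and SAP*

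**What the plan says.** Primary Objectives, item 4 of the combined protocol and SAP defines the outcome as "Patients satisfaction in achieving their goals after the procedure as assessed by Goal Attainment Scale". For this, "participants will be asked for 3 main goals that they desire to achieve after the intervention". The schedule is: "The baseline score will be (-1) and they will be interviewed again at 1, 3, 6, 9 and 12 months". The follow-up codes are -2, -0.5, 0, 1 and 2, which "will be assigned if they feel that their condition is worse than before, better but not as good as expected", as expected, better than expected, or much better than expected. For the summary, "All goals will be weighted equally, and final score will be calculated based on the available formula, in each session". The formula itself is not shown.

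Three other places bear on the point:

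- **Beginning of Study:** the study is not blinded, and a single assessor administers the measurements.
- **Study Design and the statistical analysis section:** each patient is their own control, and change is measured from the patient's own baseline.
- **Cryoneurotomy Stream, item 6:** it provides for "Reassessment of the patient post-procedure to readjust the spasticity management strategy and goals". The Pulsed radiofrequency Stream adds that "The protocol follows the same assessment and preparation as cryoneurotomy". Neither sentence mentions the Goal Attainment Scale, and the surgical streams have no such wording.

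**The concern.** Every follow-up code depends on one of two reference points. The lowest compares the patient with a remembered earlier state. The other four are defined by falling short of, meeting or exceeding an expectation. The text does not say what the expected state is for any goal, who sets it, when, or whether it is written down. It also does not say that the three scored goals are held unchanged. The baseline of -1 is assigned rather than measured, so it does not anchor the scale to an observed state.

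A within-patient design needs the same reference at every visit. If the reference lives in memory for up to 12 months, a change in score may be a change in the patient, in the expectation, or in both, and the data cannot separate them. There is no control group to show how much scores drift for reasons unrelated to the procedure, and the patient knows what was done. This is one of four primary outcomes, and the one closest to the patient satisfaction named in the Hypothesis.

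**Working it through.** The plan has no figure to reproduce for this outcome. It gives no effect size, standard deviation, significance level or power, and N = 50 is a convenience sample. The check uses the plan's own codes.

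**Inputs from Primary Objectives, item 4:** three equally weighted goals; baseline -1; better but short of expectation = -0.5; as expected = 0.

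**Step 1. One patient, all three goals.** Gain = follow-up score minus baseline.
- Rated short of expectation: -0.5 - (-1) = 0.5.
- Same physical state, expectation lowered, now rated as expected: 0 - (-1) = 1.0.
- Ratio: 1.0 / 0.5 = 2.

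If the expectation rises instead, the same patient goes from 0 back to -0.5 and the recorded gain halves. These are raw code means. Any linear formula with equal weights keeps the ratio of 2.

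**Step 2. One patient, one goal of three.** The shift in the mean is 0.5 / 3 = 0.17. Against the full step from baseline to expected (1.0), that is about one sixth.

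**Step 3. Cohort mean.** Let a share *a* of patients shift from -0.5 to 0 on all goals and a share *b* shift from 0 to -0.5. The net shift is 0.5 × (*a* - *b*). A net share of 10% gives 0.05 and 20% gives 0.10, with the sign reversed if *b* is larger. The documents give neither share, so these are illustrations only.

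**Step 4. Sensitivity of a pre-post test.** Assumptions: two-sided 0.05; a paired t-test on the score; no patient truly changes; patients who do not drift are kept at -1. (The follow-up list has no code for unchanged, so the last is also an assumption.) Because baseline is constant, the test is a one-sample test of the follow-up score against -1. Suppose 4 of 50 patients remember their earlier state as worse than it was and are scored -0.5:
- Mean change = 4 × 0.5 / 50 = 0.04.
- Variance = (4 × 0.25 - 50 × 0.04²) / 49 = 0.92 / 49 = 0.0188, so SD = 0.137.
- SE = 0.137 / √50 = 0.0194; t = 0.04 / 0.0194 = 2.06; p = 0.044.

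Four drifting patients also suffice at n = 25 (p = 0.043) and n = 10 (p = 0.037), which matters because each stream is to be analysed separately.

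**Step 5. Drift in both directions.** Simulation under the same assumptions with n = 50 (20,000 replicates) gives this chance of a false significant improvement:

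| Drift up by 0.5 | None fall to -2 | 5% fall to -2 | 10% fall to -2 |
|---|---|---|---|
| 10% of patients | about 75% | about 7% | about 0.5% |
| 20% of patients | over 99% | about 25% | about 5% |

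The result depends almost wholly on the assumed balance of drift, which the plan gives no means of knowing.

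**The case against.** The strongest reply has four parts.

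**The plan cites a published scale.** Item 4 summarises the scale and refers to an available formula; the scale's own instructions may call for written levels. That stands as a limit on wording. A reader might infer that the expectation is never recorded, but the documents support only that the plan does not say it is.

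**The readjusted goals are not shown to be the scored goals.** A reader might infer from Cryoneurotomy Stream, item 6, that the protocol lets the three goals be replaced after the procedure. It does not say so. The sentence belongs to a clinical approach published earlier, speaks of management strategy, and is followed by a remark on redistributing toxin. Item 5 of that list, on outcome measures, does not mention goal attainment. The radiofrequency cross-reference names assessment and preparation only. This part of the reply stands: item 6 shows only that the plan should state which goals it means.

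**The natural reading is that the goals stay the same, and expectations are informed.** Patients name three goals and are interviewed again about them. Every enrolled patient has had a diagnostic block, which the plan presents as a preview of the result. This is fair, but a preview is not a written expected state for each goal, and the rule still scores by feeling.

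**The outcome is labelled satisfaction, in an exploratory pilot.** Rating by feeling is therefore partly the intended construct. That lowers the stakes. It does not remove the problem, because the plan also treats the score as change from a personal baseline.

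**Conclusion.** The concern holds in limited form. The stated rule scores a primary outcome by feeling, against an earlier state and an expectation that the plan does not say are written down or held fixed. In an unblinded, uncontrolled study the recorded change can therefore move while the patient does not. Its size on the plan's codes is a doubling of the gain (0.5 to 1.0) if all goals shift from -0.5 to 0, and about 0.17 on the mean if one does. Those figures rest only on the codes and equal weights; the cohort and test figures rest on assumed drift.

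A reader might go further and conclude that the bias runs towards success. The documents do not support that: expectations may rise after early improvement and lower the score, and no rate is given in either direction. The Ashworth, Tardieu and DASH outcomes do not depend on this rule. The change is worth making because the reference state has to be written before the procedure and cannot be recovered once follow-up has begun.

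**What to change.** Replace the scoring rule in Primary Objectives, item 4.

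1. Before the procedure, write beside each of the three goals the observable current state (-1) and the expected state (0), with what counts as worse and as better, so that every code has a description. Allow -1 at follow-up for a goal that is unchanged.
2. At each visit, read those descriptions back and score the same three goals against them.
3. State that the scored goals and their levels are fixed to month 12.
4. Record any goals readjusted in clinical care separately, outside the score, and say in Cryoneurotomy Stream, item 6, that these are not the scored goals.
5. Give the summary formula.

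The cost is one baseline form and a few minutes per patient (assumption), with no extra visit, staff or patients. Some subjectivity will remain, because the interview is still unblinded, but the reference will no longer move. If overall satisfaction is wanted as well, it can be asked as a separate item.
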